5.5.5. Exploratory and Additional Efficacy Endpoints

To facilitate review of the composite endpoints in the mFAS-non-Omicron analysis set, tables will be provided summarizing medically attended visits and all-cause death, both before and after Day 29, and summarizing COVID-19-related hospital and ICU stays.

To explore efficacy and virological endpoints in the mFAS-Omicron analysis set, summary tables will be provided.

5.5.5.1. COVID-19-Related Duration of Hospitalization

For participants who did not die through Day 29, the sum of the duration of all COVID-19-related hospital stays through Day 29 will be summarized by category (>0 to <24 hours, 1-8 days, 9-15 days, 16-22 days, 23-29 days, >29 days) for each treatment group. The mean total number of days and standard deviation will also be presented. For purposes of the continuous summary, a hospital stay of less than 24 hours will be imputed as 0.5 days. A similar categorical and continuous summary will be presented for the subset of ICU stays.

The number and percentage of participants who died on or prior to Day 29 will be presented by treatment group.

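### The exploratory summary of hospital and ICU days covers only Day 29 survivors, so averting deaths can raise the mean stay in the ADG20 column

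*SAP*

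**What the plan says.** SAP 5.5.5 introduces a set of supportive tables: "To facilitate review of the composite endpoints in the mFAS-non-Omicron analysis set, tables will be provided". Within that set, SAP 5.5.5.1 takes "For participants who did not die through Day 29, the sum of the duration of all COVID-19-related hospital stays through Day 29", which "will be summarized by category (>0 to <24 hours, 1-8 days, 9-15 days, 16-22 days, 23-29 days, >29 days) for each treatment group". The lowest category is above zero; there is no row for participants with no stay.

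For the continuous version, "The mean total number of days and standard deviation will also be presented", and "a hospital stay of less than 24 hours will be imputed as 0.5 days". The section does not say whether a survivor who was never hospitalized enters the mean as zero or is left out. A similar summary is planned for ICU stays.

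The same section adds: "The number and percentage of participants who died on or prior to Day 29 will be presented by treatment group". It specifies no test, confidence interval or between-arm estimate.

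**The concern.** Survival to Day 29 is an outcome after randomization and the complement of one component of the primary endpoint (SAP 5.5.1). If ADG20 changes mortality, the two columns are no longer the randomized arms. Participants whose illness was severe enough to kill them on placebo may survive a long admission on ADG20; they are then counted in the ADG20 column while their counterparts are missing from the placebo column. The benefit appears as extra hospital days. Printing the number of deaths nearby discloses the exclusion but does not change the mean.

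The unstated denominator adds a second, conditional problem. If the mean covers only hospitalized survivors, removing short admissions leaves a longer average among those that remain. If never-hospitalized survivors count as zero, that does not happen. A programming choice could therefore decide the direction of the displayed difference.

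At stake is how a reader interprets a table meant to explain the composite endpoint, not the efficacy claim itself.

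**Working it through.** SAP 5.5.5.1 gives no expected duration or sample size, so there is no planned figure to reproduce. The mechanism can be checked on an illustrative table.

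**From the SAP.** About 320 participants in the primary efficacy population, randomized 1:1, so about 160 per arm; planning rates of 12% on placebo and a 70% relative reduction, so 3.6% on ADG20 (SAP 4.2). Stays under 24 hours count as 0.5 day (SAP 5.5.5.1) and do not meet the 24-hour hospitalization definition (SAP 3.5.1).

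**Assumed, not in the documents.** Placebo: among survivors, a = 6 short stays, b = 12 stays of 5 days, c = 4 stays of 20 days; d = 3 deaths. Primary events are 12 + 4 + 3 = 19, or 19/160 = 11.9%, close to the planning rate.

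**Formulas.**
- Total days among survivors: T = 0.5a + 5b + 20c
- Mean over hospitalized survivors: M1 = T/(a + b + c)
- Mean over all survivors, zeros included: M2 = T/(160 − d)
- Mean over all participants, death scored as 29 days lost: M3 = (T + 29d)/160
- Days alive and out of hospital, death scored 0: 29 − M3

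For placebo, T = 3 + 60 + 80 = 143.

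| Arm | a, b, c, d | T | M1 | M2 | M3 | 29 − M3 |
|---|---|---|---|---|---|---|
| Placebo | 6, 12, 4, 3 | 143 | 143/22 = 6.50 | 143/157 = 0.911 | 230/160 = 1.44 | 27.56 |
| A: averts 2 deaths only, each becoming a 20-day stay | 6, 12, 6, 1 | 183 | 183/24 = 7.63 | 183/159 = 1.151 | 212/160 = 1.33 | 27.68 |
| B: prevents the 6 short stays only | 0, 12, 4, 3 | 140 | 140/16 = 8.75 | 140/157 = 0.892 | 227/160 = 1.42 | 27.58 |
| C: roughly proportional 70% reduction | 2, 4, 1, 1 | 41 | 41/7 = 5.86 | 41/159 = 0.258 | 70/160 = 0.44 | 28.56 |
| D: uneven reduction, mostly of shorter stays | 0, 2, 3, 1 | 70 | 70/5 = 14.00 | 70/159 = 0.440 | 99/160 = 0.62 | 28.38 |

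**Reading the table.**
- A: the mean rises on both denominators. If the averted deaths become stays of 10 to 28 days, M1 is 163/24 = 6.79 to 199/24 = 8.29, and M2 is 163/159 = 1.025 to 199/159 = 1.252. All exceed placebo. M3 runs from 192/160 = 1.20 to 228/160 = 1.43, always below placebo.
- B: M1 rises and M2 falls, so the direction depends on the unstated denominator.
- C and D each have 6 primary events (4 + 1 + 1 and 2 + 3 + 1), or 3.75%, close to the planned 3.6%. C shows no artefact. D shows one in M1 only.
- M3 and days alive and out of hospital point the right way in every row.

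A and B isolate one mechanism each and leave the primary composite at 19 events (A: 12 + 6 + 1; B: 12 + 4 + 3). They show what can happen; they are not forecasts.

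**The case against.** The strongest reply is that nothing is formally compared. The table has no test or interval, duration of hospitalization is not among the endpoints in SAP Table 1, and exploratory analyses lie outside the testing hierarchy (SAP 4.4). The primary analysis counts hospitalization and death together in the full mFAS-non-Omicron set and summarizes each component. Deaths by arm appear in the same subsection, and all-cause death has its own Kaplan-Meier and Cox analyses (SAP 5.5.4). All of this stands, and it makes the point minor. It does not make the displayed mean interpretable between arms.

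Three stronger readings are tempting and are not supported:

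- **That the table describes hospitalized survivors, so preventing short admissions must lengthen the apparent stay.** SAP 5.5.5.1 names participants who did not die, not those admitted. Under the default percentage denominator in SAP 4.1 (everyone in the arm within the analysis set), fewer short stays would show as a smaller percentage, the correct direction. The short-admission effect is conditional on how the mean is computed.
- **That the over-29-days category is impossible.** For the primary endpoint, SAP 3.5.1 defines through Day 29 by the admission date. If that definition carries over, a stay admitted on Day 10 and ending on Day 45 belongs in the category. What is missing is a statement of which counting rule applies.
- **That the table will show ADG20 as worse.** Under the planned effect size, rows C and D both give a lower mean over all survivors.

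It is also fair to say that scoring every death as 0 is a value choice. The SAP, however, already treats death as an unfavourable outcome elsewhere: for symptom endpoints, participants who die are censored at Day 30, so they stay unresolved (SAP 3.5.1), and for viral clearance they count as not cleared (SAP 3.5.2).

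**Conclusion.** The point holds as a minor one. Restricting the hospital and ICU summaries to Day 29 survivors selects on a component of the primary endpoint. A drug that turns deaths into long stays can show a higher mean whichever denominator is used: in the illustration, 6.50 to 7.63 days or 0.911 to 1.151 days. The further effect from preventing short admissions exists only if the mean is limited to hospitalized survivors, which the SAP leaves open.

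The sizes rest on assumed stay lengths and death counts; the documents give none. An artefact under both denominators requires averted deaths that are not offset by fewer admissions. No confirmatory conclusion is affected.

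**What to change.** Make the change before the SAP is signed, which SAP 3.2 places before unblinding.

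1. For all mFAS-non-Omicron participants, by randomized arm, present descriptively the days alive and out of hospital for COVID-19 from Day 1 through Day 29. Score death by Day 29 as 0 and no stay as the full 29 days. Add the ICU equivalent, and state the rule for participants lost before Day 29.
2. In the existing category table, use all participants as the denominator and add a zero-day row and a died-by-Day-29 row.
3. If a mean length of stay among hospitalized survivors is kept, label it as describing that subset only.
4. State whether stays are counted to discharge or truncated at Day 29. Keep the over-29-days category if stays admitted by Day 29 are counted to discharge; stays still open at the soft lock then need a rule.

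The cost is a few sentences, one derived variable and its ICU counterpart. Protocol 6.3.2.4 already anticipates collecting visit duration and ICU admissions, and death details are on the Death eCRF (SAP 5.8.2). There are two drawbacks: the mean difference will be numerically small because most participants have no event, and scoring every death as 0 ignores when it occurred.

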5.5.5.2. Exploratory Analysis of Omicron Analysis Set

Given the expected smaller sample size of the mFAS-Omicron analysis set, the following clinical endpoints will be summarized descriptively:

- COVID-19-related hospitalization or all-cause death through Day 29
- Severe/critical COVID-19 or all-cause death through Day 29
- COVID-19-related emergency room visits, COVID-19-related hospitalization, or all-cause death through Day 29
- Time to sustained resolution of COVID-19 symptoms through Day 29
- COVID-19-related medically attended visit (telemedicine, physician office, urgent care center, emergency room, hospitalization) or all-cause death through Day 29

The following virological endpoints will be summarized descriptively unless otherwise specified:

- Change from baseline in SARS-CoV-2 viral load (\log_{10} copies/mL) to Day 7 (± 1) assessed by RT-qPCR from NP samples, apply the same methodology in Table 4.
- Viral load >5 \log_{10} copies/mL on Day 7 (± 1) based on NP samples
- Duration of SARS-CoV-2 viral shedding from Day 1 through Day 29 assessed by RT-qPCR from saliva samples
- Change from baseline in SARS-CoV-2 viral load (\log_{10} copies/mL) to Days 3, 5, 7, 11, 14, 21, and 29 assessed by RT-qPCR from saliva samples, apply the same methodology in Table 4.
- SARS-CoV-2 viral clearance (Days 3, 5, 7, 11, 14, 21, and 29) assessed by RT-qPCR from saliva samples (and BLQ/not detected or not detected for NP samples for Day 7)
- SARS-CoV-2 viral load AUC assessed by RT-qPCR from saliva samples from baseline to Day 29

5.5.6. Graphical Displays of Efficacy Endpoints

Forest plots for the standardized relative risk reduction for the primary and two binary key secondary endpoints will be provided. Additionally, adjusted, and unadjusted mean change from baseline in viral load will be depicted with forest plots, box and whisker plots and line plots.

Duration of viral shedding, time to sustained recovery of symptoms, time to symptom improvement, and time to symptom resolution will be presented using Kaplan-Meier plots and forest plots. Finally, a Kaplan-Meier plot for all-cause death will be provided.

5.5.6.1. Viral Load Effect on Adverse Clinical Outcomes

In order to identify a persistently high viral load threshold for risk of adverse clinical outcomes, the level of viral load leading to the following adverse clinical outcomes will be assessed in the mFAS-non-Omicron analysis set:

- COVID-19-related hospitalization or all-cause mortality through Day 29
- COVID-19-related emergency room visits, COVID-19-related hospitalization, or all cause death through Day 29
- Severe/critical COVID-19 or all-cause mortality through Day 29

An association between viral load (\log_{10} copies/mL) and the adverse clinical outcome will be examined graphically. The viral load for participants with the adverse clinical outcome and box plot of viral loads for participants without the adverse clinical outcome will be presented for Days 3, 5, 7, 11, 14, 21, and 29. The number and percentage of participants with and without the adverse clinical outcome will be summarized by viral load categories at Days 3, 5, 7, 11, 14, 21, and 29. Viral load from saliva samples will be used for Days 3, 5, 7, 11, 14, 21, and 29, and also from NP swabs for Day 7.

5.5.6.2. Time to Sustained Improvement of COVID-19 Symptoms Through Day 29

KM methodology will be used to analyze time to sustained symptom improvement through Day 29 (Section 3.5.1) with respect to the mFAS-non-Omicron analysis set. Median time-to improvement by treatment group and 95% CIs will be reported. Survival curves between ADG20 and placebo will be compared using a log-rank test stratified by age (categorical as 12-17, 18-65, and >65 years). A stratified Cox Proportional Hazard model will be used to estimate the hazard ratio where the model includes age (categorical as 12-17, 18-65, and >65 years) as a stratification variable and sex (categorical), baseline serostatus (categorical: positive, negative), baseline BMI (continuous) and baseline viral load (continuous as \log_{10} copies/mL) as covariates. Comparison of the survival distributions will use the score test for the hazard ratio from the Cox model. Refer to [Appendix F](#) for rules for missing symptom diary data.

5.5.6.3. Time to Sustained Recovery of COVID-19 Symptoms Through Day 29

KM methodology will be used to analyze time to sustained symptom recovery (improvement or resolution) through Day 29 (Section 3.5.1) with respect to the mFAS-non-Omicron analysis set. Median time to recovery by treatment group and 95% CIs will be reported. Survival curves between ADG20 and placebo will be compared using a log-rank test stratified by age (categorical as 12-17, 18-65, and >65 years). A stratified Cox Proportional Hazard model will be used to estimate the hazard ratio where the model includes age (categorical as 12-17, 18-65, and >65 years) as a stratification variable and sex (categorical), baseline serostatus (categorical: positive, negative), baseline BMI (continuous) and baseline viral load (continuous as \log_{10} copies/mL) as covariates. Comparison of the survival distributions will use the score test for the hazard ratio from the Cox model. A forest plot of median time to sustained symptom recovery by selected subgroups will be presented. Refer to [Appendix F](#) for rules for missing symptom diary data.

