Participant Population: Mild or moderate COVID-19 in adults and adolescents can typically be managed in the outpatient/ambulatory setting. Data from other SARS-CoV-2 mAb programs suggest that populations at high risk for progression of COVID-19 are likely to benefit from treatment with a mAb (see Section 1.4.1). In order to ensure similar risk of COVID-19 disease progression across the two treatment groups, enrollment will be stratified based on age. Data from several regions have consistently shown that age is the most critical factor for risk of severe COVID-19 including hospitalization, ICU stay, and death ([Docherty 2020](#); [Grasselli 2020](#); [Ko 2020](#); [Wu 2020](#); [Kim 2021](#)). Of the risk factors identified, age appears to have the most profound impact on outcomes, with significant increase in risk clearly evident around age 65 and a greater magnitude in risk than that associated with any individual co-morbidity ([Kim 2021](#)). In a cohort of more than 1.3 million patients diagnosed with COVID-19, of patients with no reported underlying health conditions, 9.6%, 15.5%, and 27.9% of patients 50-59, 60-69, and 70-79 years of age required hospitalization, respectively ([Stokes 2020](#)).

Symptom Onset Within 5 Days: Symptoms of COVID-19 generally appear from 2 to 14 days following exposure to SARS-CoV-2. A subset of individuals with initially mild or moderate symptoms may experience disease progression. For example, in a study of 138 hospitalized patients with COVID-19 pneumonia, dyspnea, and hospitalization developed after a median of 5 and 8 days, respectively, from symptom onset ([Wang 2020](#)). These data suggest a window for intervention of <7 days from onset of symptoms with a potently neutralizing antiviral mAb like ADG20 to prevent disease progression. Consistent with this hypothesis, experience with other highly potent mAbs (casirivimab/imdevimab, bamlanivimab/etesevimab, sotrovimab,

regdanvimab, and bebtelovimab) suggests that administration early in the course of infection (eg, within 5 to 7 days or less of onset of symptoms) is associated with faster resolution of symptoms and a reduction in the need for medically attended visits, including emergency room visits and hospitalizations ([Celltrion Healthcare Hungary 2021](#); [Eli Lilly and Company 2022a](#); [Eli Lilly and Company 2022b](#); [GlaxoSmithKline 2022](#); [Regeneron 2022](#)).

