5.6.2.1. Prohibited Concomitant Therapy

If a participant receives a prohibited concomitant medication, such as those listed below, the investigator, in consultation with the sponsor or designee, will evaluate any potential impact on receipt of study drug based on time the medication was administered, the medication's pharmacology and PK, and whether the medication will compromise the participant's safety or interpretation of the data.

The following medications are prohibited concomitant therapy. The use of prohibited concomitant medications and/or vaccines will not require withdrawal of the participant from the study.

The following agents are prohibited from randomization to Day 29:

- Investigational agents or off-label use of marketed products for the treatment of SARS-CoV-2 or COVID-19 (eg, convalescent plasma, direct acting antivirals, etc)

Note: Please refer to the *ADG20-TRMT-001 Designated Background Standard of Care* document for all prohibited therapies. This document will be updated in an ongoing manner to address changes in standard of care as additional information becomes available, such as from randomized controlled trials.

- Monoclonal antibodies to SARS-CoV-2
- Direct-acting antivirals for SARS-CoV-2 (eg, molnupiravir, nirmatrelvir/ritonavir, remdesivir)

Note: For participants who become hospitalized due to COVID-19, products for the treatment of SARS-CoV-2 or COVID-19 and/or participation in investigational treatment studies is permitted. This includes other monoclonal antibody products and direct-acting antiviral agents. Hospitalization is defined as ≥ 24 hours of acute care in a hospital or acute care facility (includes emergency rooms, intensive care units, acute care facilities created for COVID-19 pandemic hospitalization needs, or other acute care facilities). Rescue therapy for participants who are not hospitalized may be used at the discretion of the investigator if felt to be in the best interest of the participant.

- Receipt of any SARS-CoV-2 or COVID-19 vaccine prior to randomization and through Day 29 is prohibited.
- Any investigational agent or device is prohibited through 90 days after study drug administration (see note above for participants who become hospitalized).

The sponsor or designee must be notified as soon as possible of any instances in which prohibited therapies are administered.

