6.3.1.2. Saliva Collection for SARS-CoV-2 Quantitative RT-PCR

Participants will be provided with saliva sample test kits and transport packaging materials for use on Days 3, 5, 11, 14, and 21. Site staff will educate the participant on the proper collection and transport procedures. Saliva samples on Day 7 and Day 29 will be collected and transported by site staff at the in-person visits (in-clinic or home health).

On Day 1 prior to study drug administration, site staff will observe the participant collecting and packaging the saliva sample. Participants should NOT eat, drink, smoke, or chew gum for 30 minutes before all saliva sample collections.

Saliva samples will be analyzed for quantitative RT-PCR for determination of viral load, viral clearance, and duration of viral shedding and may be used for viral sequencing.

In the event that a participant is hospitalized during the Follow-Up Period, saliva collection should be continued if feasible. If access to a participant by parent/guardian/LAR/family member/other or site staff is not possible, engagement of a local home health care visit can be considered per local regulations.

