To evaluate the effect of ADG20 on SARS-CoV-2 viral load and clearance in participants with mild or moderate COVID-19 and high risk of disease progression	
Change from baseline in SARS-CoV-2 viral load (\log_{10} copies/mL) to Day 7 (± 1) assessed by RT-qPCR from NP samplesViral load $> 5 \log_{10}$ copies/mL on Day 7 (± 1) based on NP samplesDuration of SARS-CoV-2 viral shedding from Day 1 through Day 29 assessed by RT-qPCR from saliva samplesChange from baseline in SARS-CoV-2 viral load (\log_{10} copies/mL) to Days 3, 5, 7, 11, and 14 assessed by RT-qPCR from saliva samplesSARS-CoV-2 viral clearance (Days 5, 7, 11, 14, 21, and 29) assessed by RT-qPCR from saliva samples (and BLQ/not detected or not detected for NP samples for Day 7)SARS-CoV-2 viral load AUC assessed by RT-qPCR from saliva samples from baseline to Day 29
To evaluate the long-term safety and tolerability of ADG20 compared to placebo in participants with mild or moderate COVID-19 and high risk of disease progression	
Assessment of safety based on:
 
The incidence of TEAEsChanges from baseline in clinical laboratory tests (ie, CBC with differential, serum chemistry, coagulation)Changes from baseline in vital signs (body temperature, heart rate, respiration rate, and systolic and diastolic blood pressure)
To evaluate the PK of ADG20 following IM administration	PK parameters of ADG20: As data permit, C_{max} , T_{max} , AUC_{0-last} , AUC_{0-inf} , CL, Vd, and $T_{1/2}$. Additional PK parameters may be calculated
To evaluate the immunogenicity (ADAs) to ADG20	Incidence of ADAs against ADG20
To evaluate the emergence of resistance to ADG20	Genotypic characterization of viral isolates for reduced susceptibility to ADG20, with phenotypic evaluation as appropriate
Exploratory	
To evaluate the effect of host or viral biomarkers on clinical outcomes	Effect of baseline SARS-CoV-2 specific antibody response on select clinical outcomes
To identify a persistently high viral load threshold for risk of adverse clinical outcomes	
The level of viral load leading to the following adverse clinical outcomes:
 
COVID-19-related hospitalization or all-cause death through Day 29COVID-19-related emergency room visits, COVID-19-related hospitalization, or all-cause death through Day 29Severe/critical COVID-19 or all-cause death through Day 29

Objectives	Endpoints

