3.5.1. Clinical Efficacy Endpoints

COVID-19-related hospitalization or all-cause death through Day 29 (primary endpoint):

COVID-19-related hospitalizations include visits for attention to worsening signs or symptoms attributed to COVID-19, in the opinion of the investigator.

- **Hospitalization** is defined as ≥ 24 hours of acute care in a hospital or acute care facility (includes emergency rooms, intensive care units, acute care facilities created for COVID-19 pandemic hospitalization needs, or other acute care facilities).
- **Through Day 29** is defined as the admission date for the hospitalization or acute care facility occurring from Day 1 (postdose) up to and including Day 29.
- **All-cause death** is defined as death for any reason from Day 1 (postdose) through Day 29.

Severe/critical COVID-19 or all-cause death through Day 29: All-cause death is defined as death for any reason from Day 1 (postdose) through Day 29. Severity is based on the investigator's assessment of severity (eCRF COVID-19 Severity Assessment) per the following protocol definitions:

- **Severe COVID-19** is defined as having a positive test by standard RT-PCR assay or equivalent test plus the following:
 - Symptoms suggestive of severe systemic illness with COVID-19, which could include any symptom of moderate illness or shortness of breath at rest, or respiratory distress including the need for initiation of oxygen therapy.
 - Clinical signs suggestive of severe systemic illness with COVID-19, such as respiratory rate ≥ 30 breaths per minute, heart rate ≥ 125 beats per minute, $\text{SpO}_2 \leq 93\%$ on room air at sea level or ratio of arterial oxygen partial pressure to fractional inspired oxygen ($\text{PaO}_2/\text{FiO}_2$) < 300 mm Hg.
 - No criteria for critical severity.
- **Critical COVID-19** is defined as having a positive test by standard RT-PCR assay or equivalent test plus evidence of critical illness, defined by at least one of the following:
 - Respiratory failure based on resource utilization requiring at least one of the following:

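### The exploratory viral-load threshold analysis does not require the load to precede the outcome; from Day 11 onward most loads in participants with the outcome would be taken after the event

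*SAP*

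**What the plan says.** The exploratory endpoint in SAP section 2 (Table 1) is worded causally: "The level of viral load leading to the following adverse clinical outcomes". SAP 5.5.6.1 repeats the aim: "the level of viral load leading to the following adverse clinical outcomes will be assessed in the mFAS-non-Omicron analysis set". It names three composites through Day 29: hospitalization or death; emergency room visit, hospitalization or death; and severe/critical COVID-19 or death.

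On sampling it says: "Viral load from saliva samples will be used for Days 3, 5, 7, 11, 14, 21, and 29", with the Day 7 nasopharyngeal (NP) swab used as well. Participants are split by whether they had the outcome. Loads are plotted by day for each group, and then "The number and percentage of participants with and without the adverse clinical outcome will be summarized by viral load categories at Days 3, 5, 7," and so on to Day 29.

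SAP 3.5.1 counts a hospitalization by "the admission date for the hospitalization or acute care facility occurring from Day 1 (postdose) up to and including Day 29". Sampling does not stop at admission. Protocol 6.3.1.2 says: "In the event that a participant is hospitalized during the Follow-Up Period, saliva collection should be continued if feasible". I found no landmark, at-risk restriction or comparison of event date with sample date, in 5.5.6.1 or elsewhere.

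**The concern.** A threshold for risk has to come from loads measured before the event. As written, a participant admitted on Day 4 supplies a load among those with the outcome on Days 5, 7, 11, 14, 21 and 29, and all six follow the admission.

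Loads taken after the event may also differ for reasons unrelated to prior risk. Once a participant is hospitalized for COVID-19, protocol 5.6.2.1 lifts its restriction on other COVID-19 products: "This includes other monoclonal antibody products and direct-acting antiviral agents". In-hospital saliva is collected only where feasible, and there is none after death. The severe/critical composite inherits the problem, because SAP 3.5.1 imputes that status for anyone who meets the primary endpoint.

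At stake is the meaning of one exploratory result. Tables described as showing the load that leads to an outcome will be read as prognostic, and the later days would not be.

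**Working it through.** The plan gives no figure for this point, so there is none to reproduce. The check has three steps.

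**1. The Day 29 column, with no timing assumption.** The outcome window closes on Day 29. The protocol schedule (Table 12-1) allows the Day 29 visit from Day 29 to Day 34. A sample at that visit cannot precede an in-window event, except possibly one on the same day. SAP Appendix B (Table 10) maps Days 24 to 34 to this visit, so only an unscheduled sample on Days 24 to 28, used when the nominal one is missing, could come first.

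**2. Median admission day from the protocol's figures.**
- Onset to admission: median 7 days (protocol 1.2) or 8 days (protocol 1.3.2: "hospitalization developed after a median of 5 and 8 days, respectively, from symptom onset"). Both sections describe a study of 138 hospitalized patients; I use both values.
- Symptom duration at randomization: 0 to 5 days (protocol 3.1).
- Study day of median admission = median − symptom days + 1, taking dosing on the day of randomization.

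| Median | 5 symptom days at entry | 0 symptom days at entry |
|---|---|---|
| 7 | 7 − 5 + 1 = Day 3 | 7 − 0 + 1 = Day 8 |
| 8 | 8 − 5 + 1 = Day 4 | 8 − 0 + 1 = Day 9 |

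The result is Day 3 to 9, always before Day 11. For a participant admitted then, all four scheduled loads on Days 11, 14, 21 and 29 follow admission.

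**3. Share of hospitalizations before each sampling day.** The documents give no distribution of admission day for this trial. Assumptions: lognormal onset-to-admission time, median 7 or 8, log-SD 0.35 to 0.7; symptom duration uniform over 0–5 or 2–5 days; only admissions after randomization and through Day 29 count. Exclusion criterion 1 (protocol 4.1.2) bars anyone expected to need hospitalization within 48 hours, so I also ran the case with all first-48-hour admissions removed, as if that prediction were perfect.

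| | Before Day 7 | Before Day 11 |
|---|---|---|
| All admissions after randomization | 50–79% | 73–97% |
| First 48 hours removed | 41–73% | 68–96% |
| Combined range | 41–79% | 68–97% |

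A wider grid (log-SD 0.3 to 0.7; symptom duration fixed at 0, 3 or 5 days, or uniform over 0–5) gives 17–92% at Day 7, 64–99% at Day 11, 78–100% at Day 14, 94–100% at Day 21 and essentially all at Day 29.

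A deliberately unfavorable case, admission day uniform over Days 1 to 29, gives 36% at Day 11, 47% at Day 14, 71% at Day 21 and 100% at Day 29, or 63% over the four days together.

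**In numbers of participants.** SAP 4.2 gives about 320 participants and a blinded aggregate rate of about 9%: 0.09 × 320 = 28.8, about 29 with the primary outcome, all treated here as hospitalizations.
- Events still to come at Day 11: 29 × (1 − 0.97) ≈ 1 to 29 × (1 − 0.68) ≈ 9.
- Events still to come at Day 7: 29 × (1 − 0.79) ≈ 6 to 29 × (1 − 0.41) ≈ 17.

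These shares refer to scheduled samples. If in-hospital samples are missed, the share among loads actually obtained could be lower, and the loads that remain are a selected set.

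**The case against.** The strongest reply is that little depends on this analysis. It is listed as exploratory, it examines an association graphically and with counts, and it has no model, test, estimated cut-off or decision rule. Loads of participants with the outcome are shown apart from the box plot of those without. SAP 5.5.4 plans listings of viral load and of medically attended visits, and SAP 4.1 has dated listings show study day, so a reader could work out which loads followed admission. All of that stands and limits the importance of the point. It does not repair the tables, which as specified pool loads from before and after the event under a heading about risk.

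A second reply is that a persistently high load needs serial measurements, which a single-day landmark does not supply. That is fair: the filter does not define persistence. But serial loads used to define it must still precede the event.

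Third, the timing rests on assumed distributions and on medians from patients already hospitalized. This also stands, and it is why Day 7 is left open.

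A reader might infer three stronger things that the documents do not support:
- *That most events fall in the first study week, so the analysis fails from Day 7.* The range of 41–79% straddles one half, and the wider grid gives 17–92%.
- *That the Day 7 NP cut-offs of 5 and 4 log10 copies/mL are compromised.* They are fixed in advance for a separate secondary comparison between arms (SAP 3.5.2 and Table 4); 5.5.6.1 neither derives nor uses them.
- *That in-hospital treatment lowers these participants' loads and so biases the threshold downward.* The protocol permits such treatment after admission but does not say how often it is used, and protocol 1.2 and 1.3.2 describe availability as limited. Both the direction and the size of any effect are unknown.

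**Conclusion.** The point holds for SAP 5.5.6.1. Followed exactly, the plan relates loads on seven days to an outcome at any time through Day 29, so it cannot show from the later days which load led to the outcome. The missing ordering rule and the Day 29 problem are visible in the documents without any timing assumption. That most loads from Day 11 are post-event follows from the protocol's medians together with the assumed lognormal timing (68–97% of hospitalizations before Day 11). It weakens at Days 11 and 14 if admissions were spread evenly over the month. Day 7 is undetermined.

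The problem concerns loads from the roughly 29 participants with the primary outcome, not those without it, but those participants are the ones who would define any threshold. Primary and key secondary inference is unaffected. The change is worth making because it is cheap, not because the trial's main conclusions depend on it.

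**What to change.** In SAP 5.5.6.1, for each outcome and each sampling day:
- include only participants alive and free of that outcome at the sample date;
- count only outcomes with onset after the sample and through Day 29;
- show the number of events remaining at that day;
- display loads taken on or after the event date separately, flagged as post-event and not used for the threshold.

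One added sentence should say which date counts as onset for each composite, in particular for severe/critical status, which may come from a visit assessment or be imputed from the primary endpoint.

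The cost is SAP wording and a filter on event date against sample date, with no new data collection. It should be settled before the unblinding described in SAP 3.2. The small downside is that few or no events will remain at the later days, which is an accurate statement of what those samples can tell.
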